6.1.2 Planned Number of Sites and Patients

The study will be conducted at multiple locations in the USA, Australia, or elsewhere as appropriate. Each site must have the capacity to conduct point of care COVID-19 RT-PCR test from NP swabs with a turn-around time no more than 48 hours. Sites must have access to point of care G6PD testing or be able to receive G6PD test result from an in-house or commercial laboratory within 48 hours. Sites must have pharmacy with capability to dispense study medication in secondary child-proof containers with appropriate labelling.

Approximately 275 patients with COVID-19 will be enrolled with the goal of reaching 250 patients meeting the mITT criteria at the end of the study.

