6.1.3 Randomization

Eligible patients will be randomized at 1:1 ratio to receive TQ or placebo and stratified by site. Randomization will be performed through a centralized, web-based, validated system that automates the assignment of patients to treatment assignment. The randomization scheme will be reviewed and approved by the sponsor or designee. For study medication dispensation, the Investigator or designee will access the randomization system to determine which blinded study medication bottle the patients will be assigned.

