12.1 General Statistical Considerations

Statistical hypothesis testing will be performed at two sided alpha level of 0.05. For continuous variables, population size (N for sample size and n for available data), the mean, the standard deviation (SD), the median, the minimum and maximum values will be tabulated. For categorical variables, number and percentage in each category will be tabulated.

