12.3 Planned Efficacy Analyses

12.3.1 Analysis of the Primary Efficacy Variable

The proportion of patients with clinical recovery at Day 12 will be analyzed using two methods: a 2x2 contingency table and logistic regression. The contingency table will provide unadjusted estimates of the proportions of patients with clinical recovery at Day 12. Copper-Pearson exact 95% confidence intervals around the recovery proportion within each treatment group will be provided. If 95% or more patients on the TQ arm have clinically recovered, then no logistic regression will be performed due to too few events then a Fisher's exact test will be used to compare treatment groups. However, if the rate is less than that then a logistic regression will be utilized. Treatment group will be the primary independent factor in the logistic regression. Additional covariates will be included in the model for every 10 events observed (eg, if at least 20 events then clinical site will be included, at least 30 events dichotomized number of symptoms (1-2 vs 3-4). Selection of additional covariates will be based on their relationship to the primary endpoint and correlation with other covariates. Patients who do not have a Day 12 visit due to hospitalization for COVID-19 symptoms will be considered treatment failures.

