12.6 Determination of Sample Size

The sample size calculation is based on the primary endpoint of recovery rate.

In a study of nonhospitalized patients with COVID-19 disease reported by [Skipper \(2020\)](#), placebo treated patients had resolution of clinical symptoms of COVID-19 by Day 14 in 70% of patients. Assuming an 85% clinical recovery rate in the TQ group and a 70% clinical recovery rate in the placebo group, sample sizes of 125 per treatment group will achieve 80% power with a two-sided alpha of 0.05 by logistic regression analysis.

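### Section 12.3.1 charges clinical site as one covariate under its 10-events rule, although as an ordinary factor it costs one parameter fewer than the number of sites

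*Combined protocol and SAP*

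**What the plan says.** Section 12.3.1 sets the size of the primary model by the number of events, with further covariates entering "for every 10 events observed (eg, if at least 20 events then clinical site will be included". It gives the next slot, at 30 events, to a two-level symptom count. Treatment uses the first 10 events, so site is given exactly one slot.

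The section does not define an event. The fallback to Fisher's exact test when at least 95% of the tafenoquine arm has recovered is explained by saying that "no logistic regression will be performed due to too few events". That makes sense only if events are non-recoveries.

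Site is a design factor. Section 6.1.3 says: "Eligible patients will be randomized at 1:1 ratio to receive TQ or placebo and stratified by site". Section 6.1.2 says: "The study will be conducted at multiple locations in the USA, Australia, or elsewhere as appropriate". No section gives or caps the number of sites, and none describes pooling of small sites, random site effects, or a stratified or conditional analysis. Section 12.3.2 carries the primary method over to the dichotomous secondary endpoints.

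**The concern.** A rule of 10 events per covariate is meant to keep the model small enough for ordinary maximum likelihood to behave. It works only if it counts parameters. A factor with K sites is one variable but K − 1 parameters, so the rule lets in a model that its own standard would refuse. When many small sites are fitted as fixed effects, two things follow. The treatment odds ratio is pushed away from 1 if there is a true effect, and the Wald and likelihood-ratio tests become somewhat liberal. Both worsen as the same 250 patients are spread over more sites. A secondary endpoint with only 20 to 30 events would admit site where the miscount bites hardest.

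**Working it through.** **Inputs.** Section 12.6 gives the rates ("Assuming an 85% clinical recovery rate in the TQ group and a 70% clinical recovery rate in the placebo group") and the size ("sample sizes of 125 per treatment group will achieve 80% power with a two-sided alpha of 0.05 by logistic regression analysis"). Section 12.1 gives the two-sided alpha of 0.05. The number of sites K is an assumption, taken over the range 2 to 50.

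**The plan's own figure.** The design odds ratio is (0.85/0.15)/(0.70/0.30) = 2.43, log 0.887. For a treatment-only logistic model, SE = √[1/(125×0.85×0.15) + 1/(125×0.70×0.30)] = √(0.0627 + 0.0381) = 0.318. Then 0.887/0.318 − 1.96 = 0.83, which gives power of 79.8%. The stated 80% reproduces.

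**Expected events.** Non-recoveries: 125×0.15 + 125×0.30 = 56.25.

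**Parameter count** (intercept excluded). At the 20-event trigger, treatment plus site has 1 + (K − 1) = K parameters. With symptom count added it has K + 1.

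| Sites K | 20 events: 20/K | 56.25 events: 56.25/(K+1) |
|---|---|---|
| 2 | 10 | 18.8 |
| 3 | 6.7 | 14.1 |
| 4 | 5 | 11.3 |
| 5 | 4 | 9.4 |
| 10 | 2 | 5.1 |
| 20 | 1 | 2.7 |

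The standard of 10 is missed from K = 3 at the trigger and from K = 5 at the expected events.

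**Effect on the analysis.** Two simulations of 250 patients used permuted blocks of 4 within site and site as a fixed factor.
- A: uneven site sizes, site SD 0.5 on the logit, treatment plus site, null recovery 77.5%; 16,000 null and 2,000 alternative trials per setting.
- B: equal site sizes and the section 12.3.1 rule (symptom count at 30 or more events, Fisher fallback). Null recovery was 70%, 85% or 90%, with site SD 0 or 0.5; the alternative used SD 0.5. There were 10,000 trials per setting.

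The Monte Carlo SE on type I error is about 0.2 points in each. The type I columns give the span over Wald and likelihood-ratio tests and, for B, over the null rates as well.

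| K | Type I, A | Type I, B | Median OR, A | Median OR, B |
|---|---|---|---|---|
| 2 | – | 4.5–5.4% | – | 2.46 |
| 5 | – | 4.1–5.5% | – | 2.50 |
| 10 | 5.4–5.6% | 4.4–5.7% | 2.51 | 2.56 |
| 20 | 5.9–6.2% | 5.1–6.3% | 2.62 | 2.66 |
| 30 | 6.7–7.0% | 5.9–7.2% | 2.75 | 2.79 |
| 50 | – | 6.7–8.6% | – | 3.13 |

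In B the null estimate was centred on an odds ratio of 1 at every K.

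**Site-stratified comparison.** In B, the Cochran-Mantel-Haenszel (CMH) test held 4.4–5.4% at every K from 2 to 50, with a median Mantel-Haenszel odds ratio of 2.42–2.43 and power of 79–80%. In A its type I error was 5.1%, 5.1% and 5.4% at 10, 20 and 30 sites. A further run gave 2.55 and 2.66 at 10 and 20 sites with site as a fixed factor, against 2.46 and 2.48 by Mantel-Haenszel.

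**The case against.** The strongest reply is that this is under-specification rather than a demonstrated fault. The rule is introduced as an example, section 12 defers full methodology to a SAP, and nothing says that site must enter as ordinary fixed effects. That stands as a limit: the consequences hold only if site is fitted that way. It does not remove the miscount, because the one worked example in the plan charges site as a single covariate and no alternative handling is described.

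Several stronger readings are tempting and are not supported.
- *The primary test exceeds 5% type I error.* The documents do not give the number of sites. At 10 or fewer the excess is nil to about 0.7 points, and an excess of about 1 point needs about 20 sites. Falling below 10 events per parameter does not by itself mean material inflation.
- *The bias favours tafenoquine.* Under the null the estimate stays centred on 1. The shift is away from 1 and appears only when there is a true effect.
- *The model would carry K + 3 parameters.* That fills all five slots with covariates. The plan names only site and symptom count, so K + 1 is the supportable count.
- *Sites where every patient has the same outcome damage the treatment estimate.* They contribute nothing to it in the fixed-effect model, and nothing under stratification either, so they do not separate the plan from the fix.

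The meaning of event also matters. If recoveries were meant (250 − 56.25 = 193.75), the K + 1 model would miss the standard only from 19 sites (193.75/20 = 9.7). The Fisher clause points to non-recoveries, but the plan should say so.

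**Conclusion.** The rule miscounts site, and this follows from the text and simple counting. It meets its own standard at the 20-event trigger only with 2 sites, and at the expected 56 events only with up to 4. These thresholds assume that events are non-recoveries and that site is an ordinary factor.

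The practical harm depends on the unstated number of sites. Relative to 2.43, the simulation B medians are about 3% too high at 5 sites (2.50/2.43), 5% at 10 (2.56/2.43), 9–10% at 20 (2.66/2.43) and 15% at 30 (2.79/2.43). Type I error is close to nominal up to about 10 sites and modestly raised at 20 to 30. Adjusting for site is itself right, since randomisation is stratified by it, and the sample size statement is not in error. The rule should be corrected before the SAP is final; the documents do not show the primary test to be invalid.

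**What to change.** In the SAP:
- Handle site as the randomisation stratum in the primary test: CMH stratified by site, reported with the Mantel-Haenszel odds ratio. If covariates are kept, use conditional logistic regression stratified by site, which estimates no site parameters. Only CMH was simulated here, so the operating characteristics of the conditional model should be checked at the planned number of sites.
- Define an event as the rarer outcome, non-recovery.
- Count parameters, not variables, toward the 10-events rule for any remaining covariates. With site stratified out, treatment plus symptom count is two parameters, or at most 56.25/2 ≈ 28 events each.
- State the planned number of sites.

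The cost is small. Section 12 allows changes to statistical methods in the SAP before database lock and unblinding without a protocol amendment. Single-outcome sites contribute nothing, as they already do in the fixed-effect model. Apparent power falls by about 0 to 3 points with up to 30 sites. In simulation B at 30 sites, CMH gave 79.4% against 82.6% for Wald (83.2% for likelihood-ratio). Part of that gap is the liberal type I error being removed, and power stays at about the planned 80%.

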⁵ After resting for 3 minutes the number of breaths will be taken over one minute.

⁶ The severity of shortness of breath will be reported by the patient using the Modified Borg Scale for Grading the Severity of Dyspnea shown in [Section 15.2.1](#).

⁷ The severity of coughing will be reported by the patient using the Cough Severity Scale shown in [Section 15.2.2](#).

⁸ Prior medications used in the 14 days prior to the start of screening will be recorded.

⁹ Hematology tests include: WBC count, absolute neutrophil count, RBC count hematocrit, hemoglobin, platelet count; C-reactive protein, INR, PT/PTT.

¹⁰ Clinical chemistry tests include: BUN, creatinine, ALT and AST.

¹¹ Study drug will either be dispensed in the clinic, if the patient has a clinic visit on Day 1, or will be delivered by same day courier service to the patient at home on Day 1, after final eligibility has been determined the patient is randomized.

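### The primary logistic model is not fixed in advance: further covariates are chosen by their relation to the outcome, and the screening cough grade and Borg dyspnea score are not pre-specified

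*Combined protocol and SAP*

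**What the plan says.** Section 12.3.1 makes treatment the main factor and lets one more covariate in for every 10 events. Site (at least 20 events) and "at least 30 events dichotomized number of symptoms (1-2 vs 3-4" are given as examples, not as a closed list. The next sentence reads "Selection of additional covariates will be based on their relationship to the primary endpoint and correlation with other covariates". No candidate list, threshold or algorithm follows, and nothing says whether selection is blind to treatment. Section 12.3.2 applies the same method to the dichotomous secondary endpoints.

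Section 4.1 defines recovery by temperature, respiratory rate, absence of shortness of breath, and cough no worse than mild. Section 6.1 and Table 1 have cough and dyspnea graded at screening. For dyspnea, a Table 1 footnote says "The severity of shortness of breath will be reported by the patient using the Modified Borg Scale". Neither score is named as a covariate or a stratification factor. On allocation, Section 6.1.3 says "Eligible patients will be randomized at 1:1 ratio to receive TQ or placebo and stratified by site".

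Section 12 defers full methods to an SAP to be finalised before database lock and unblinding. The document supplied contains no separate SAP text.

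**The concern.** There are two linked issues.

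**Pre-specification.** The number of covariates depends on the observed event count, and their identity depends on their relation to the primary endpoint. The model behind the primary p-value can therefore not be written down before outcomes are seen.

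**The severity measure.** The endpoint is graded but the named covariate is not. Section 7.1 admits a patient on a new cough of any grade. A patient with only a mild cough, normal temperature, normal respiratory rate and no dyspnea already satisfies the recovery definition at entry. A patient with severe cough and intense dyspnea must improve on both. If those are the second patient's only symptoms, both fall in the 1-2 group. (The protocol does not list the symptoms counted. A maximum of four fits the four recovery components.)

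At stake are a primary analysis that can be audited against a plan, and some precision if baseline grade is prognostic.

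**Working it through.** **Inputs from the protocol.** Section 12.1: "Statistical hypothesis testing will be performed at two sided alpha level of 0.05". Section 12.6: "Assuming an 85% clinical recovery rate in the TQ group and a 70% clinical recovery rate in the placebo group", and "sample sizes of 125 per treatment group will achieve 80% power with a two-sided alpha of 0.05 by logistic regression analysis". Section 6.1.2 plans 275 enrolled to reach 250 in the mITT population.

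**1. The plan's own power, with treatment only.**
- Log odds ratio: ln[(0.85/0.15)/(0.70/0.30)] = ln 2.43 = 0.887.
- SE: √[1/(125×0.70×0.30) + 1/(125×0.85×0.15)] = √(0.0381 + 0.0627) = 0.318.
- Power: Φ(0.887/0.318 − 1.96) = 79.8%. The pooled two-proportion formula gives 81.4%.

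The stated 80% reproduces and contains no covariate.

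**2. How many terms the plan's rule allows.** The protocol does not define an event. Its remark about too few events when 95% or more recover implies non-recovery.
- Expected failures: 125×0.30 + 125×0.15 = 37.5 + 18.75 = 56.25.
- SD: √(125×0.30×0.70 + 125×0.15×0.85) = √42.2 = 6.5.
- The 30-event condition lies (56.25 − 30)/6.5 = 4.0 SD below the mean, so at the design rates the symptom count will almost surely enter.
- 56/10 gives about five terms: treatment, site (if it counts as one), symptom count and about two more. The open rule could therefore admit cough grade and Borg score. It neither requires nor excludes them.

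**3. What a graded score might add.** The documents give no prognostic strength, so these are assumption-based ranges. Simulation: 125 per arm, marginal rates 70% and 85%, 4,000 runs per setting, one graded score, and a dichotomised count whose latent correlation with it is 0.4 or 0.7 (the two values in each cell). The Monte Carlo SE is √(0.82×0.18/4000) = 0.6 points.

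| Assumed OR per SD | Unadjusted, % | Dichotomised count, % | Graded score, % | Gain over count |
|---|---|---|---|---|
| 1.0 | 81.7, 82.5 | 81.7, 82.2 | 81.3, 82.4 | about 0 |
| 1.65 | 80.8, 81.8 | 80.9, 82.2 | 82.2, 83.2 | about 1 |
| 2.7 | 81.5, 81.3 | 82.1, 82.5 | 86.1, 86.8 | about 4 |
| 4.5 | 82.7, 81.6 | 83.1, 84.2 | 91.0, 91.2 | 7 to 8 |

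A second simulation (3,000 runs) also gave each symptom its own effect, a log-odds of 0.5 (assumed). With severity at 0.5 per SD (OR 1.65), power was 82.2% with the dichotomised count, 82.7% with the ungrouped count and 84.1% with count plus severity. At 1.0 per SD (OR 2.7) it was 81.4%, 81.7% and 87.0%. Gains over the dichotomised count are thus 1.9 and 5.6 points. Ungrouping the count alone adds only 0.3 to 0.5.

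**4. Whether the choice of model can decide the result.** Four models were fitted to the same simulated trials: count alone, count plus either severity score, and count plus both (2,000 runs per setting, 70% vs 85%). With an assumed log-odds of 0.3, 0.5 or 0.8 per SD for each score, the four models disagreed on significance in roughly 5%, 7% and 10% of trials.

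**The case against.** A reader might infer that the baseline scores are unused, or that the plan adjusts only for the count. The documents do not support this: site is also named, the list is by example, and the rule leaves room for about two more covariates. The accurate description is that the scores are not pre-specified.

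The power gain is set by assumption. It is nil if the scores are not prognostic and about 1-2 points if they are weakly so. That grade predicts recovery is an inference from two of four endpoint components. Power was about 80% or higher in every simulated setting, even unadjusted. Leaving out a prognostic covariate does not invalidate a randomised comparison. This all stands. So does the point that the 1-2 versus 3-4 cut costs little in itself.

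A reader might also infer that the selection rule inflates the type I error. That is not shown. The rule refers to a covariate's relation to the endpoint, not to its effect on the treatment estimate, and it could be applied blind to treatment or settled from prior knowledge. The difficulty is that the text does not say.

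Deferral to a later SAP is a fair reply on missing detail. It does not fully answer here, because the selection sentence is a stated rule that a later SAP would have to withdraw.

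Two practical objections also hold. Day 1 scores are not stated to be taken before dosing, and for telemedicine patients they are home eDiary entries on the dosing day. Site could also exhaust the term budget: with five sites (an assumption, since the number is not stated), treatment plus site already takes five terms. The simulations contain no site term and a single severity score, so they only approximate the recommended model.

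**Conclusion.** The concern holds as one of pre-specification with a possible loss of efficiency. Section 12.3.1 leaves the primary model open and selects covariates by their relation to the outcome, while two graded measures tied directly to the endpoint are collected at screening and not named. No stated figure is wrong and the planned test is not invalid. The power at issue ranges from 0 to about 8 points, wholly according to an assumed prognostic strength. Independently of average power, permitted models can disagree on significance in roughly 5% to 10% of trials under the assumptions in step 4. A change before unblinding is worthwhile because it is nearly free.

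**What to change.** In the SAP, before unblinding:

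- Fix the primary model as treatment, screening cough grade, screening Borg score, symptom count and site. Use screening values, which clearly precede treatment.
- Enter cough grade and Borg score as one linear term each. Treatment, count, cough and Borg then take four of the roughly five terms that 56 failures allow under the plan's own rule.
- Handle site by a stated rule: pool small sites, or use a method stratified by site, so that it does not use up the remaining budget.
- Delete the sentence on outcome-based selection, define an event as non-recovery, and carry the fixed model to the dichotomous secondary endpoints. Ungrouping the symptom count is optional.

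No new data or visits are needed. The costs are SAP wording, a few more terms against about 56 expected failures, and an odds ratio that is conditional on the covariates rather than marginal. The unadjusted proportions already planned for the 2×2 table would still be reported beside it.

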-------------------------------	--

	
(4) Receipt of any experimental treatment for COVID-19 (off-label, compassionate use, or study-related) within the 30 days prior to the time of the screening evaluation(5) Any excluded concomitant medication as described in the ARAKODA package insert [Section 15.1](6) Any COVID-19 symptoms which, in the opinion of the investigator, is suggestive of possible requirement to hospitalize within 48 hours of enrollment(7) Positive pregnancy test(8) Have been symptomatic for more than five days when the first dose would be administered
Treatment Groups:	There will be 2 treatment groups; TQ and placebo for which at least 250 patients will be randomized in 1:1 ratio to treatment with clinical site as a stratification variable. Randomizations will continue until at least 250 patients meet the criteria for mITT.
Screening Procedures:	After signing informed consent, patients will be screened for eligibility including medical history, G6PD, RT-PCR for SARS-CoV-2, pregnancy testing for females of child-bearing potential, hematology, blood chemistry, vital signs, O ₂ saturation, and physical exams. The Screening period will be a maximum of 4 days (Days -4 to -1), and the first day of dosing will be Study Day 1.
Randomization Procedure:	Eligible patients will be randomized at a 1:1 ratio to receive TQ or placebo. Randomization will be performed through a centralized, web-based, validated system that automates the assignment of patients to treatment allocation. Randomization will be stratified by clinical site.
Efficacy Assessments:	
• Clinical signs and symptoms of COVID-19 (clinically diagnosed and patient reported) including fever, shortness of breath, cough, and respiratory rate daily from Day 1 to Day 28 (Note, the clinical signs of COVID-19 will not be reported as AEs)• SARS-CoV-2 PCR at Day 12 ± 1 day.• Hospitalization

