	
Primary Efficacy Endpoint:
 
The proportion of patients with clinical recovery at Day 12 will be analyzed using two methods: a 2x2 contingency table and logistic regression. The contingency table will provide unadjusted estimates of the proportions of patients with clinical recovery at Day 12. Copper-Pearson exact 95% confidence intervals around the recovery proportion within each treatment group will be provided. In a logistic regression treatment group will be the primary independent factor, additional covariates will be included in the model if there are sufficient events. Patients who do not have a Day 12 visit due to hospitalization for COVID-19 symptoms will be considered treatment failures
 
Other Efficacy Endpoints:
 
Dichotomous secondary endpoints will be analyzed in the same manner as the primary endpoint. The number of medical follow-up visits tabulated to determine if the endpoint can be considered continuous or ordinal. If the data are continuous the treatment groups will be compared by t-test. If the frequency distribution indicates few numbers of visits (e.g., 0, 1, 2, and 3 visits) then the analysis will use a chi-squared test to compare treatment groups.
 
Safety Endpoints:
 
AEs will be coded using the most recent version of the Medical Dictionary of Regulatory Activities (MedDRA) preferred terms and will be grouped by system, organ, and class (SOC) designation. The incidence of new COVID-19 symptoms not present at screening will be reported separately from other AEs including the maximum severity and time of maximum severity relative to the start of investigational product. The severity, frequency, and relationship of AEs to investigational product will be presented by preferred term by SOC grouping. Listings of each individual AE including start date, stop date, severity, relationship, outcome, and duration will be provided. Each AE (based on preferred terminology) will be counted once only for a given patient. If the same AE occurred on multiple occasions, the highest severity and relationship to investigational product will be assumed. Thus, study participants are not counted multiple times in a given numerator in the calculation of frequencies for a specific AE. Laboratory data and vital signs will be reported as summary statistics and change from baseline by treatment group for the safety population.
 
Justification of Sample Size:
 
Assuming an 85% clinical recovery rate in the TQ group and a 70% clinical recovery rate in the placebo group, sample sizes of 125 per treatment group will achieve 80% power with a two-sided alpha of 0.05 by logistic regression analysis.

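### The primary logistic model is not fixed in advance: covariates beyond site and symptom count are unnamed and chosen by their relationship to the endpoint, and site, the only randomisation stratum, enters only by event count

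*Combined protocol and SAP*

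**What the plan says.** Section 12.3.1 (Analysis of the Primary Efficacy Variable) puts treatment in a logistic regression and then lets the model grow with the data: "Additional covariates will be included in the model for every 10 events observed". Two steps are given, introduced as examples. For site, the rule is "if at least 20 events then clinical site will be included". A symptom count split at 1-2 versus 3-4 follows at 30 events. For anything further the rule is "Selection of additional covariates will be based on their relationship to the primary endpoint and correlation with other covariates". No candidate list, association threshold or order of entry is given.

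The Synopsis names no covariate: "additional covariates will be included in the model if there are sufficient events".

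Site is the only stratification factor, both in the Synopsis ("Randomization will be stratified by clinical site") and in section 6.1.3 ("Eligible patients will be randomized at 1:1 ratio to receive TQ or placebo and stratified by site"). The number of sites is not given; section 6.1.2 says "The study will be conducted at multiple locations in the USA, Australia, or elsewhere as appropriate".

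The test itself can also change: "If 95% or more patients on the TQ arm have clinically recovered, then no logistic regression will be performed due to too few events". Fisher's exact test is used in that case.

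Section 12.3.2 applies the primary approach to the dichotomous secondary endpoints. Section 12 describes the methods in general terms and defers the complete description to an SAP due before database lock and unblinding. The documents supplied contain no later text that replaces the rule in 12.3.1.

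**The concern.** A primary analysis should be reproducible from the plan. Here an analyst who follows 12.3.1 exactly must still decide which covariates to consider, how to measure their relationship to the endpoint, and how much correlation with other covariates rules one out. Because the sentence follows a rule based on observed events, it is most naturally read as selection on this trial's own outcome data. In logistic regression the treatment odds ratio and its p-value both change with the covariates in the model, so these choices feed into the primary result.

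A second, smaller issue is that the one factor used to stratify randomisation is included only if enough events occur. The usual principle is that a stratification factor belongs in the analysis whatever the event count.

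**Working it through.** **Inputs.** From section 12.6: recovery 85% (TQ) and 70% (placebo), 125 per arm, two-sided alpha 0.05. From section 12.3.1: thresholds of 20 events (site) and 30 events (symptom count), one slot per further 10 events, and Fisher's test at 95% TQ recovery. The plan does not define an event. Non-recovery is assumed, as the too-few-events reason for the 95% rule implies.

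**The plan's own figure.** For an unadjusted Wald test, n = (1.960 + 0.842)² × [1/(0.85×0.15) + 1/(0.70×0.30)] / (ln 2.43)² = 7.849 × 12.605 / 0.787 = 125.7 per arm. Power at 125 is 79.8%. The stated 125 and 80% therefore match a model with treatment only, and the sample size is not in question.

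**How many unnamed slots open.** Events follow Binomial(125, 0.15) + Binomial(125, 0.30), with mean 18.75 + 37.5 = 56.25. If the two examples are taken as the actual order, unnamed slots = floor(events/10) − 3.

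| Events | Unnamed slots | Probability |
|---|---|---|
| under 40 | 0 | 0.004 |
| 40–49 | 1 | 0.145 |
| 50–59 | 2 | 0.546 |
| 60–69 | 3 | 0.282 |
| 70 or more | 4 or more | 0.023 |

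So P(at least one unnamed slot) = 0.996.

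**What the open choice does (simulated, all covariate inputs assumed).** Two analysts each list 6 of 12 candidates, of which 4 are prognostic at log-odds 0.3–0.5 per SD, with correlation 0–0.3. Each ranks by pooled association and fills the slots allowed (4000 runs per setting; site not simulated).
- Verdicts at 0.05 differ in 3.8–5.8% of trials at 85%/70% and in 1.6–2.6% under no effect.
- With one shared list and four selection rules, verdicts differ in 1.0–1.8% at 85%/70%. The missing list matters most.
- Each analyst's type I error is 4.6–5.6%. A separate simulation (6 candidates, 5 sites, 70% recovery in both arms) gave 5.1–5.2% for selection blind to treatment, against 4.9% for a fixed model.

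**When site would be left out.** At 85%/70%, P(fewer than 20 events) = 1.6 × 10⁻¹⁰. At higher recovery (TQ/placebo) it is 0.12 at 90%/90%, 0.36 at 93%/90%, 0.58 at 95%/90% and 0.97 at 95%/95%.

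For an uncommon secondary outcome with pooled rate h (assumed range), P(Binomial(250, h) ≤ 19) is:

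| h | Fewer than 20 events | 95% rule sends the analysis to Fisher |
|---|---|---|
| 2% | 1.00 | 0.99 |
| 4% | 0.997 | 0.77 |
| 6% | 0.88 | 0.37 |
| 8% | 0.47 | 0.12 |
| 10% | 0.12 | 0.03 |

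The last column is P(Binomial(125, h) ≤ 6), since 95% of 125 is 118.75 and so at most 6 TQ patients may have the outcome. An ordinary Fisher's test does not account for site either.

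Under no effect with 10 sites (site SD 0.5–1.0 on the log-odds scale, assumed), omitting site gave rejection rates of 3.4–4.6%, against about 5% for a site-stratified test.

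**The Fisher trigger (minor).** P(Binomial(125, 0.85) ≥ 119) = 0.0003. At 119/125 versus 110/125 there are 6 + 15 = 21 events, yet Fisher is required (p = 0.066; unadjusted Wald p = 0.047). At 118/125 versus 125/125 there are only 7 events and an empty cell, yet logistic regression is required.

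**The case against.** The strongest reply is deferral. Section 12 calls itself general and promises a complete SAP before unblinding, so a list may exist that cannot be seen here, and a trial has one SAP rather than two analysts drawing separate lists. This stands as a limit: the two-analyst comparison only illustrates how far the wording leaves the result open. It does not remove the point, because 12.3.1 states an actual selection rule, and an SAP that repeated it would leave the model just as open.

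Several other replies are right:
- The text says relationship to the primary endpoint and does not expressly say in the observed data. Prior knowledge is not excluded, although trial data is the natural reading.
- The 0.996 is the chance that a slot opens. Whether a covariate fills it also depends on its association and its correlation with the others.
- The symptom count has no stated time point. However, its categories have no zero, and the inclusion criteria require at least one symptom around screening, so baseline is the sensible reading.

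A reader might infer that selection by association inflates the false-positive rate. The documents do not support that. Selection blind to treatment kept type I error near 5%. Only a choice made with treatment results in view raised it, to about 6–10% across the simulations, and nothing in 12.3.1 licenses that. A reader might also infer that the primary analysis will ignore the stratification factor. At the planned rates it will not.

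**Conclusion.** The point holds as a pre-specification defect that should be fixed. At the design rates the plan almost certainly opens one or more slots for covariates it does not name, to be filled by an outcome-driven rule with no list and no cut-off. Confidence is high on the wording and on the event counts, which rest only on the plan's rates, on non-recovery as the event and on the examples as the order of entry. The size of the effect on verdicts, a few percent of trials at most, rests on assumed covariates.

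The site condition is secondary. It has no practical effect on the primary endpoint at planned rates. It can omit site when recovery is well above plan or for uncommon secondary outcomes, where the 95% rule often leads to an unstratified Fisher's test instead. The consequence is a somewhat conservative test, not an inflated one. The Fisher trigger does not track its stated reason but is a minor matter, since it almost never fires at 85%.

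**What to change.** In the SAP, before unblinding:

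1. State one primary model: treatment, site always accounted for, and the already named symptom count (1-2 versus 3-4) at baseline. Logistic regression conditional on site is one suitable form, with small sites pooled by a rule based on enrolment only.
2. Delete the sentence that selects covariates by their relationship to the endpoint. Put any others in a sensitivity analysis with a list fixed in advance.
3. For the dichotomous secondary endpoints, keep site as a stratum whatever the event count, and use a site-stratified test when events are few.
4. Optionally, let the exact-test fallback depend on an empty cell or non-convergence rather than on TQ-arm recovery alone.

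**Cost.** SAP text only, with no extra patients or data. Section 12 says such changes need no protocol amendment, and the Synopsis can be aligned at the next one. A pooling rule must be written, and sites where every patient has the same outcome add nothing to a conditional estimate. In simulation (10 and 20 sites, 1000 runs per setting) power at 85%/70% was 82.7–84.6%, against 83.7–86.7% for the plan's rule coded with site indicators and without unnamed covariates. That gives up about 1–2 points of nominal power.
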